1.6 Trial registration - Trial identifier and registry name

The Australian New Zealand Clinical Trials Registry (ANZCTR), U1111-1260-0960

2. SYNOPSIS

TITLE	The effectiveness of Rapid Syllable Transition Treatment in
	improving communication in children with cerebral palsy: A
	randomized controlled study
	,
PRIMARY HYPOTHESIS	That ReST will be more effective in improving speech
	intelligibility and communicative participation with children with
	CP than usual care.
DESIGN	Single blind cross over randomised controlled trial
BLINDING/MASKING	Single blind
	As a behavioural intervention trial, the treating clinicians and
	participants cannot be blinded to allocated group or
	intervention.
OUTCOMES	The primary outcome
	Speech intelligibility in single words
	Secondary outcomes
	1 Communicative norticipation
	 Communicative participation Parent / Carer and child satisfaction in their child's
	communicative participation
	3. Speech accuracy
	4. Sentence complexity and length in speech and AAC use
STUDY DURATION	Estimated study duration from enrolment until completion of
	data analyses 8 months
INTERVENTION/S	Rapid Syllable Transition Treatment. (ReST)
NUMBER OF PARTICIPANTS	20, 10 per group.
POPULATION	Sample Size: n=20
	Gender: Male and female
	Age : Children aged between /y0m - 14y11m
	Demographic group: N/A Diagnosis: Corobral Palsy
	Diagnosis. Celebrar Paisy
	1) Aged between 8-14 years
	2) Diagnosis of CP
	3) Viking Speech Scale classification II-III
	4) No diagnosis of intellectual disability
	5) Normal or adjusted-to-normal hearing and vision

3. RATIONALE / BACKGROUND

3.1 Background

Cerebral palsy (CP) is a group of disorders of movement and posture caused by damage to the developing brain (Rosenbaum et al., 2007). Communication disorders, such as difficult to understand speech, referred to as dysarthria, are common in cerebral palsy (Andersen et al., 2010). Dysarthria is a group of neurological speech disorders that results from abnormalities in the strength, speed, range, steadiness, tone, or accuracy of movements and impacts on the control of the respiratory, phonatory, resonator, articulatory, and prosodic aspects of speech production (Duffy, 2013). There are different severity levels of dysarthria which are described with the Viking Speech Scale (VSS; Pennington et al., 2010). VSS level 1 represents very mild dysarthria, while VSS 4 refers to the most severe form of dysarthria. Reduced speech intelligibility impacts on communicative participation, which is the ability to participate in daily conversations, make social connections and friendships (Mei et al., 2014). Although speech intelligibility promotes successful communicative participation, the exact role intelligibility plays in communicative participation it is not currently well understood (Baylor & Darling-White, 2020).

Current interventions aimed to improve speech for children with CP include; interventions that focus on voice, such as Lee Silverman Voice Treatment, LSVT LOUD (Boliek, et al, 2017); interventions that are based on speech subsystems theory, referred to as Speech Systems Intelligibility Treatments (SSIT; Pennington, et. al., 2010, 2013); and PROMPT therapy which focuses on realigning oral musculature to improve speech (Ward, 2014). These interventions have been demonstrated to improve speech intelligibility with children with CP (Pennington, et. al., 2005), although there is currently no evidence to suggest which of these is more effective, especially with children with significant dysarthria, such as VSS levels II and III.

Neuroplasticity is the ability of the central nervous system (CNS) to change and adapt in response to environmental cues, experience, behavior, injury, or disease (Ludlow et al, 2008). According to the principles of neuroplasticity only what is practised will be leant. Accordingly, intervention should be intensive and consist of frequent opportunities to practise the intervention target. Motor speech interventions that adhere to these neuroplasticity principles should include frequent and exclusive practice of the target behavior, namely speech sounds.

Rapid Syllable Transition Treatment (ReST; McCabe et al., 2017) is a motor speech intervention that deliberately uses the principles of motor learning. Although ReST was designed for children with childhood apraxia of speech, it may provide an alternative speech intervention for children with CP as it uses principles of motor learning. Its suitability for children with CP was trialed in the pilot study preceding this study and was noted to produce positive gains in speech and communication skills in children with significant dysarthria (Korkalainen et al., 2020).

ReST involves the use of multisyllabic pseudowords to improve the ability to transition rapidly and fluently from one sound/syllable to the next, and control of the melody in the form of relative emphasis, or stress, placed on each syllable within a word (McCabe et al., 2017).

Page 6 of 21 The effectiveness of Rapid Syllable Transition Treatment in improving communication in children with cerebral palsy: A randomized controlled study

3.2 Rationale for Study

The current motor speech interventions for children with CP, namely LSVT LOUD, SSIT, and PROPMT are based on the Speech Subsystems approach. The Speech Subsystem approach emphasizes the role of the resonatory, phonatory, resonatory, and articulatory subsystems in speech production. The lowest subsystem level is respiration followed by phonation, resonance, and lastly articulation (Hayden & Square, 1994). Speech interventions based on the Speech Subsystems approach start intervention at the lowest speech subsystem level and progress to the higher levels once mastery at each level is obtained (Hayden & Square, 1994). ReST provides an alternative motor speech intervention approach because of its adherence to the principles of motor learning. Rather than focusing on the speech subsystems, it emphasizes the importance of practising the target behavior, specifically speech sounds. Although ReST has not been studied with children with CP, the promising results from the pilot study on using ReST with children with CP (Korkalainen, et. al., 2020) and it's close attention on the principles of motor learning warrant further investigation.

4. AIMS / OBJECTIVES / HYPOTHESES

Aim:

The study aims to investigate if Rapid Syllable Transition Treatment (ReST) is effective in improving speech intelligibility and communicative participation in children with cerebral palsy (CP).

Hypotheses:

- 1. ReST will be more effective in improving speech intelligibility in children with CP than usual care
- 2. ReST will be more effective in improving communicative participation in children with CP than usual care.

6. STUDY DESIGN

6.1 Type of Study

This is a single blind cross-over randomised controlled trial. The children are randomised to the ReST group first or usual care first.

Page 7 of 21 The effectiveness of Rapid Syllable Transition Treatment in improving communication in children with cerebral palsy: A randomized controlled study

6.2 Schedule of Events/ Treatment Phases

Table 1: Flowchart of the schedule of events

- 1. Rolling Recruitment: Please see section 6.4.1
- 2. Eligibility Screening: Participants will participate a screening assessment via teleconferencing. This will take 10 15 minutes.
- 3. **Baseline Assessment, T1**: All eligible participants will attend an initial assessment in person at the University speech pathology clinic or at the family's home. If this is not possible, the assessment will be conducted on teleconference.
- 4. The Consent form will be signed.
- 5. **Randomisation**: The children who are eligible to participate will be randomised to ReST first- group or usual care- group.
- 6. Treatment phase 1:
 - a. **ReST first- group:** Children in the treatment group will receive ReST therapy three times a week for six weeks, totalling 18 sessions.
 - b. Usual care- group: Children in the usual care group will continue their usual care therapy and complete T2 and T3 assessments. See Table 1, The Flowchart of the schedule of events. The content and dosage of usual care will be recorded. If the participant has a speech generating device, the frequency of use and device satisfaction will also be recorded.
- 7. **Treatment phase 1 Post intervention assessment, T2**: Within one week after the final ReST session.
- 8. **Treatment phase 1 Follow up assessment, T3:** Three weeks after the final ReST session.
- 9. Treatment phase 2:
 - a. **ReST first- group:** The children will complete T4 and T5 assessments.
 - b. **Usual care- group:** Children in the usual care group will commence ReST after T3 assessments are completed. See Table 1, The Flowchart of the schedule of events.
- 10. **Treatment phase 2 Post intervention assessment, T4**: Within one week after the final ReST session.
- 11. **Treatment phase 2 Follow up assessment, T5**: Three weeks after the final ReST session.

6.3 Population / Sample size including power calculation

Sample size:

The sample size will be 20 children, 10 in each group.

Sample size calculation:

Sample size calculator used: https://www.ai-therapy.com/psychology-statistics/sample-size-calculator)

This pilot RCT is the first to use ReST with children with CP in a randomised controlled trial. There are no previous studies of this intervention with this population using the proposed outcome measures from which sample sizes could be calculated, so studies with similar populations, treatments, and measures were considered for sample size calculations. ReST is a motor speech intervention for the treatment of childhood apraxia of speech (CAS). While it has been shown to be effective in improving speech in children with CAS, it has not been researched with children with CP. Our exploratory pilot study on the use of ReST with children with CP indicated improvement in mean length of utterance, with a d2 effect size of 0.56. This effect size gives a sample size of 6. This was derived from calculating the effect sizes from the group means (baseline and maintenance), and standard deviation for four outcome measures. Speech MLU is a secondary outcome in the current study ReST effect sizes have primarily been calculated using d2. Using this metric, Thomas (2017) reported an average ReST intervention effect size of 5.55 (SD 2.41, range 2.48-8.52). (Previously published single-case clinician-delivered ReST treatment studies reporting similar dependent measures; McCabe et al., 2014; Thomas et al., 2014; Thomas et al., 2016). Using this effect size with a power of 0.8 and alpha of 0.05 the online sample size calculation produced a sample size of **3 for each group**. The only other RCT using ReST in children with CAS produced an effect size (Cohen's d) of 1.376 giving a sample size of 10 for each group.

The other motor speech interventions used with children with CP include LSVT LOUD (Boliek & Fox, 2017), Speech Systems Intelligibility Treatment (Pennington et al., 2010; 2013), and PROMPT (Ward, 2012). Sample size calculations were derived for each of these studies.

LSVT LOUD: Boliek & Fox, 2017 reported a Cohen's d effect size of 0.3 for pre and post speech intelligibility measures. The sample size calculation was therefore a sample size of 52.

Speech Systems Intelligibility Treatment: Effect sizes were not reported in these studies, so they were calculated from the published study data. These were (Pennington et al., 2010) Cohen's d effect size of - 0.5 and (Pennington et al., 2013) 0.6 respectively. The sample size calculation was based on these provided sample sizes of 19 and 23 respectively.

PROMPT: Ward (2012) reported a Cohen's d effect size for the percentage of phonemes correct each of the four children. The mean of these was 1.1. The sample size calculation was therefore 7.

The sample size figures calculated from the non-ReST studies on children with CP were notably larger than those based on the ReST treatment studies. Although studies on children with CP may require a large sample size due to their heterogeneity, a sample size that is too large may be presumptuous at this stage as the effectiveness of ReST with children with Cerebral palsy is not known. Besides, the interventions in these studies differed quite significantly from ReST intervention, which may render the sample sizes improbable. In the absence of previous comparable studies on the effectiveness of ReST in children with CP, studies with other populations using ReST, studies with CP population using different interventions, and an exploratory study on ReST with CP population were considered in sample size calculations. Based on these, and our best estimate, a sample size of six per group was satisfactory. This was increased to ten per group to account for potential attrition and to reflect the calculation from Murray et al. (2015) study on the effectiveness of ReST.

Page 10 of 21 The effectiveness of Rapid Syllable Transition Treatment in improving communication in children with cerebral palsy: A randomized controlled study

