6.7.3 Participant Replacement following withdrawal

Replacements will not be sought for participants who withdraw from the study, as attrition has been accounted for in our sample size calculations.

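### Several sample-size figures in section 6.3 do not follow from their effect sizes, including the base figure of six, and ten per group has no attrition margin on the one between-group effect that supports it

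*Protocol*

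**What the plan says.** Section 6.3 lists effect sizes from several sources, each with a sample size.

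- **ReST pilot in cerebral palsy (mean length of utterance, a secondary outcome):** reported "with a d2 effect size of 0.56. This effect size gives a sample size of 6". On its origin the protocol says "This was derived from calculating the effect sizes from the group means (baseline and maintenance), and standard deviation for four outcome measures", so it is a pre-post effect.
- **Single-case ReST studies:** d2 5.55, giving 3 per group. This is the only calculation with its settings stated: "Using this effect size with a power of 0.8 and alpha of 0.05".
- **ReST randomised trial in childhood apraxia of speech:** Cohen's d 1.376, giving 10 per group.
- **LSVT LOUD:** pre-post d 0.3. "The sample size calculation was therefore a sample size of 52".
- **Two Speech Systems Intelligibility Treatment studies:** d of -0.5 and 0.6. "The sample size calculation was based on these provided sample sizes of 19 and 23 respectively".
- **PROMPT:** mean d 1.1, giving 7.

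The section concludes that "a sample size of six per group was satisfactory". It continues: "This was increased to ten per group to account for potential attrition", and gives as a second reason agreement with the childhood apraxia trial. Section 6.7.3 then states: "Replacements will not be sought for participants who withdraw from the study, as attrition has been accounted for in our sample size calculations".

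**The concern.** A standardised difference of 0.56 is moderate, and six children per group is far too few to detect it with 80% power. The pilot is the only ReST evidence in children with cerebral palsy that the section uses, and six is where the design starts. The two Speech Systems figures also run the wrong way: the larger effect is given the larger sample. Finally, ten per group is asked to do two jobs, to match the childhood apraxia calculation and to absorb attrition.

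Two things are at stake. Readers are told that 6 to 10 per group is adequate for effects for which it is not. And an operational rule, no replacement of withdrawals, is justified by a margin that needs a sound base figure to exist.

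**Working it through.** **Inputs.** Effect sizes and stated sizes are those of section 6.3. Power 0.80 and alpha 0.05 are stated there for d2 5.55 only and are assumed for the rest. Sidedness is not stated, so both are shown.

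**Method.** Exact noncentral-t solutions, rounded up. As a hand check, the two-sided normal approximation uses (1.960 + 0.842)² = 7.849:
- two groups: n per group = 2 × 7.849 / d²
- paired: n = 7.849 / d²

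**Figures that reproduce as two-group sizes**
- d 5.55: 2.02, so 3 per group, as stated.
- d 1.376: 9.36 two-sided, so 10 per group, as stated. One-sided it would be 7.31, so 8. The stated 10 is therefore the two-sided figure.

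**All figures (two-sided / one-sided)**

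| Effect | Stated n | Two-group, per group | Paired | Reproduces? |
|---|---|---|---|---|
| 5.55 | 3 | 3 (two-sided) | not needed | yes, two-group |
| 1.376 | 10 | 10 / 8 | 7 / 5 | yes, two-group two-sided |
| 0.56 | 6 | 52 / 41 | 28 / 22 | no |
| 0.3 | 52 | 176 / 139 | 90 / 71 | no |
| 0.5 (absolute) | 19 | 64 / 51 | 34 / 27 | no |
| 0.6 | 23 | 45 / 36 | 24 / 19 | approximately, paired two-sided only |
| 1.1 | 7 | 15 / 11 | 9 / 7 | paired only |

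**Hand checks**
- d 0.56: two groups 2 × 7.849 / 0.3136 = 50.06, so 51; paired 7.849 / 0.3136 = 25.03, so 26.
- d 0.6, paired: 7.849 / 0.36 = 21.8, so 22. The stated 23 lies between this and the exact 24.
- d 1.1, paired: 7.849 / 1.21 = 6.49, so 7. The one-sided paired t-test also gives 7 (6.69).

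**The six.** Reading d2 as d squared gives d = √0.56 = 0.748, which needs 30 per group two-sided or 23 one-sided (paired 17 or 13). Six per group reaches 80% power only at d of about 1.80 two-sided or 1.54 one-sided. At d 0.56, six per group has 14% power two-sided.

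**The order of 19 and 23.** Under any one method, n falls as |d| rises. A size of 19 for |d| 0.5 and 23 for 0.6 cannot come from the same method.

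**Attrition.** Going from 6 to 10 leaves room to lose 4 of 10 per group, but only if six is sufficient. Measured against d 1.376, the requirement is 9.36, rounded up to 10. Two-sided power at d 1.376 is 82.9% with 10 per group, 78.2% with 9 and 72.6% with 8. An allowance on top of ten would give 10/0.90 = 11.1, so 12 per group, at 10% loss, and 10/0.80 = 12.5, so 13, at 20%. These loss rates are assumptions; the protocol gives none.

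**What ten per group detects.** On an unadjusted two-sided two-group t-test with complete data, the smallest d with 80% power is about 1.33. Power is 22% at d 0.56, 25% at 0.6, 64% at 1.1 and 83% at 1.376.

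**The case against.** **Sidedness.** The hypotheses are directional and no sidedness is stated. One-sided, power at d 1.376 is 87% with 9 per group and 83% with 8, which would leave some margin. But the protocol's own 10 is reproduced by the two-sided calculation; one-sided, it would have been 8. The point stands for the calculation as printed, and it is a reason to state the sidedness.

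**Swapped or rounded figures.** The one-sided paired size at d 0.6 is 19, and an unrounded 0.54 would give 23, so 19 and 23 may simply have been transposed. Similarly, 52 is the one-sided paired size at d 0.35. These explanations are possible but unproven. The figures as printed still fail.

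**Another route to six.** Six can be reached if 0.56 is converted first. For example, an assumed pre-post correlation of 0.9 turns it into 0.56 / √0.2 = 1.25 on the within-child scale, for which a one-sided paired test needs 6. The protocol states no such step, and the result would be a single-group pre-post size, not six per group.

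**The planned analysis is stronger than a t-test.** Section 6.14 plans a repeated-measures ANOVA, and baseline data can reduce residual variance. With an assumed baseline correlation of 0.7, baseline-adjusted power with 10 per group is about 90% at d 1.1 and about 38% at 0.56. The t-test figures must therefore carry the name of the test. Section 6.3 claims no such gain, and even a fully paired analysis of all 20 children has only 66% power at a within-child d of 0.56.

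**The protocol is partly candid.** It calls the study a pilot, says that no comparable studies exist, notes that the cerebral palsy studies gave larger sizes and describes the choice as a best estimate. This stands, and it lowers the risk that a null result is misread, but it does not make the arithmetic right.

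**Conclusion.** The point holds for specific figures. Six does not follow from 0.56: the requirement is 41 to 52 per group, or 22 to 28 paired. The 52 does not follow from 0.3 (paired 71 to 90, two-group 139 to 176), nor the 19 from |d| 0.5 (paired 27 to 34, two-group 51 to 64). The 7 and, approximately, the 23 are paired pre-post sizes and cannot be read as per-group sizes for a comparison of two groups. Ten per group has no attrition margin over the d 1.376 requirement.

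Three stronger readings are not supported.

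- A reader might infer that the whole calculation is wrong. The 3 and the 10 reproduce, and the 10 matches the size chosen.
- A reader might infer that no attrition allowance was made at all. On the protocol's own reasoning the step from six to ten is an allowance; it fails because six is unsupported.
- A reader might infer that the trial itself can detect only d of about 1.33 or more. That limit belongs to an unadjusted two-sided t-test. The planned analysis may do better by an amount the protocol does not quantify.

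The conclusion assumes power 0.8 and alpha 0.05 throughout, and holds for the six, the 52 and the 19 whichever sidedness is taken.

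**What to change.** Keep 20 children and restate the justification.

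In section 6.3:
- Delete the claim that d2 0.56 yields a sample size of 6, and the conclusion that "a sample size of six per group was satisfactory".
- Correct or remove the 52 and the 19. Check the 23 and whether the pair was swapped. Label the 23 and the 7 as paired pre-post sizes.
- State the test, the sidedness, and the power and alpha used for every figure.
- State that, for an unadjusted two-sided two-group t-test with complete data, 10 per group gives 80% power only for d of about 1.33 or more, with 22% at 0.56, 25% at 0.6, 64% at 1.1 and 83% at 1.376. Add that the planned repeated-measures analysis may do better by an unquantified amount.

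In section 6.7.3, remove the statement that attrition is accounted for. Give the power at d 1.376 on the same test with 9 and 8 per group: 78% and 73%.

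The cost is protocol wording only, with no extra children. The stated power becomes less favourable.

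### The sample size of 6 that section 6.3 attaches to the pilot effect of 0.56 does not follow from it, which removes the support for six per group and for the attrition reserve

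*Protocol*

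**What the plan says.** Section 6.3 converts a series of published or pilot effect sizes into sample sizes with an online calculator. Power and alpha are given once, for the single-case ReST studies in childhood apraxia: "Using this effect size with a power of 0.8 and alpha of 0.05 the online sample size calculation produced a sample size of" 3 per group, from an effect of 5.55. Sidedness is not stated. The other entries are:

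- ReST pilot in CP, mean length of utterance: "with a d2 effect size of 0.56. This effect size gives a sample size of 6". On its origin the section says: "This was derived from calculating the effect sizes from the group means (baseline and maintenance), and standard deviation for four outcome measures".
- Earlier randomised trial of ReST in apraxia: d 1.376, giving 10 per group.
- LSVT LOUD in CP, pre to post, d 0.3: "The sample size calculation was therefore a sample size of 52".
- Two studies of systems-based speech therapy in CP, d of -0.5 and 0.6: "The sample size calculation was based on these provided sample sizes of 19 and 23 respectively".
- PROMPT in CP, mean d over four children: "The mean of these was 1.1. The sample size calculation was therefore 7".

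The section then contrasts the two sets of studies: "The sample size figures calculated from the non-ReST studies on children with CP were notably larger than those based on the ReST treatment studies". Weighing all of them with the team's best estimate, it concludes that "a sample size of six per group was satisfactory". Six is raised to ten per group for attrition and to match the earlier apraxia trial. Section 6.7.3 declines to replace withdrawals because the sample size already allows for attrition.

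**The concern.** For a fixed test, alpha and power, the required sample size falls as the effect grows. The printed list does not behave this way: 0.5 is given 19 but the larger 0.6 is given 23, and 0.56 is given 6 while 1.1, about twice as large, is given 7. The entry that looks furthest out is 0.56 to 6, and it matters most because it is the only printed calculation equal to the size the section settles on before adding a reserve.

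Two later statements depend on that six. One is the attrition allowance, which is the gap between 6 and 10. The other is the contrast between CP studies and ReST studies, in which the pilot counts as a ReST study needing few children.

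**Working it through.** **Inputs.** Effect sizes and printed sample sizes from section 6.3. Alpha 0.05 and power 0.8 are stated there for one entry and assumed for the rest. Sidedness is not stated, so both are tried.

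**Formulas.** Noncentral t. For two groups of n, the noncentrality is d·√(n/2) on 2n − 2 degrees of freedom. For n children tested pre and post, it is d·√n on n − 1 degrees of freedom. The required n is the smallest that reaches power 0.8.

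**Reproducing the protocol's own figures first.** Two groups, two-sided: d 1.376 gives 10 per group (power 0.829) and d 5.55 gives 3 per group. Both match, so the method fits the calculator where the protocol says per group.

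**The 0.56 entry.** A normal approximation gives the scale:
- two groups: 2 × (1.960 + 0.842)² / 0.56² = 15.70 / 0.3136 = 50.1, so 51 per group
- pre-post: 7.85 / 0.3136 = 25.0, so 26 in total

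The exact t results are 52 per group (41 one-sided) and 28 in total (22 one-sided). Even with power cut to 0.5, the two-sided pre-post test needs 15. Turned round, a sample of 6 has 80% power only for d of about 1.43 (pre-post, two-sided), 1.19 (pre-post, one-sided) or 1.80 (6 per group, two-sided).

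**All entries.**

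| d | printed | two-group, per group, two-sided / one-sided | pre-post, total, two-sided / one-sided | result |
|---|---|---|---|---|
| 5.55 | 3 per group | 3 / 2 | 3 / 3 | reproduces |
| 1.376 | 10 per group | 10 / 8 | 7 / 5 | reproduces |
| 1.1 | 7 | 15 / 11 | 9 / 7 | reproduces as one-sided pre-post |
| 0.6 | 23 | 45 / 36 | 24 / 19 | within one of two-sided pre-post |
| 0.56 | 6 | 52 / 41 | 28 / 22 | fails |
| 0.5 | 19 | 64 / 51 | 34 / 27 | fails at face value |
| 0.3 | 52 | 176 / 139 | 90 / 71 | fails at face value |

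**Consequence for the reserve.** Two-group, two-sided power:
- 6 per group: 0.142 at d 0.56 and 0.576 at d 1.376
- 9 per group: 0.782 at d 1.376
- 10 per group: 0.220 at d 0.56 and 0.829 at d 1.376

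The effect detectable with 80% power is 1.80 with 6 per group and 1.33 with 10 per group. On the 1.376 basis, ten is the full requirement, and losing one child per group takes power just below 0.8.

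**Consequence for the contrast.** On either basis the pilot sits among the CP studies with d 0.5 to 0.6: 52 per group against 45 to 64, or 28 in total against 24 to 34 (two-sided). The apraxia studies stay well below, at 3 and 10 per group.

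**The case against.** There is a fair case for reading the section more kindly, and much of it stands.

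- **Most of the list may be sound.** A reader might infer that the whole table is wrong. It is not: two entries reproduce exactly, a third reproduces as a one-sided pre-post test, and a fourth is within one child. The CP effects are printed to one decimal. Solving a one-sided pre-post test backwards, n of 7, 19, 23 and 52 correspond to d of 1.07, 0.593, 0.535 and 0.349, which round to 1.1, 0.6, 0.5 and (only just) 0.3. If 19 and 23 were transposed, all four CP entries fit one test. This is an inference, since the protocol gives neither sidedness nor unrounded effects. It does not rescue 0.56 to 6.
- **The cause is unknown.** It is tempting to call the 6 an arithmetic slip. The effect is labelled d2, the metric that also yields 5.55, and is described as drawn from four outcome measures, so a wrong input or mixed metric is equally possible. The text supports only that 6 does not follow from 0.56.
- **Ten per group has its own basis.** A reader might infer that the enrolled size collapses with the six. It does not: ten is also tied to d 1.376, and that step is correct. The six is also said to rest on best estimate, although no other printed calculation gives it.
- **The two-group gap overstates the like-for-like one.** The 0.56 is a baseline-to-maintenance effect, so 22 to 28 against 6 is the fair comparison; 52 answers a different design question. The trial is also a crossover analysed by repeated measures. If 0.56 is taken as a standardised difference between treatments in a crossover, the total needed is 28, 18, 13 or 8 for an assumed within-child correlation of 0.5, 0.7, 0.8 or 0.9. A repeated-measures ANOVA can return 6 in total if, for example, 0.56 is read as Cohen's f with correlation 0.5 at five or six time points. The protocol states none of these assumptions, and 6 in total would still not be six per group.
- **The contrast is partly true.** It holds against the apraxia studies, and the section gives a second reason for discounting the CP studies, namely that the interventions differed. Deleting it would go too far.

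**Conclusion.** The point holds for the pilot entry and what hangs on it. An effect of 0.56 needs 28 children in total pre-post (22 one-sided), about four to five times the printed 6, or 52 per group in a two-group comparison. This assumes that alpha 0.05 and power 0.8 apply to the entry, as stated for its neighbour, and that 0.56 is a standardised mean difference. The six-per-group conclusion then has no printed calculation behind it. The reserve between 6 and 10 is not a reserve: six per group has 58% power even at d 1.376, and ten is simply the number that effect requires.

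The 0.3, 0.5 and 0.6 entries need rechecking and should not be declared wrong, because rounding and a transposition may account for them. The ordering and the unlabelled mixture of designs are defects of presentation on any reading. The 22% power of ten per group at d 0.56 describes a two-group comparison and is not the power of the planned repeated-measures or crossover analysis, which may be higher. The documents do not support the stronger readings that ten per group is unfounded or that the protocol claims 80% power for the pilot effect. It calls itself a pilot trial and notes that mean length of utterance is a secondary outcome.

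**What to change.** Amend sections 6.3 and 6.7.3, with no change to enrolment:

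1. Correct the sample size attached to 0.56 or, if the effect size or metric was the wrong input, correct that and show the calculation.
2. Recheck the 0.3, 0.5 and 0.6 entries against unrounded effects, including whether 19 and 23 are transposed. Label every figure as pre-post or two-group, one- or two-sided, total or per group. Do not force pre-post effects into a two-group formula.
3. Remove the statement that six per group was satisfactory, and the claims in sections 6.3 and 6.7.3 that attrition is covered by the calculation.
4. Limit the contrast with the CP studies to the ReST studies in apraxia, and say that the ReST pilot in CP needs about as many children as the CP studies with d of 0.5 to 0.6.
5. State that ten per group gives 80% power in a two-group, two-sided comparison only for d of about 1.33 or more, and about 22% at 0.56. Add that the repeated-measures or crossover analysis may do better, depending on a within-child correlation that would have to be stated.

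The cost is protocol wording and a short recalculation. The stated justification becomes less favourable, resting on the apraxia trial's effect and on the study's pilot character.
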